### During Surgery

- Mechanical or surgical manipulation required to enlarge the pupil
- Vitreous loss (significant)
- Anterior chamber bleeding (significant)
- Uncontrollable positive intraocular pressure
- Complications in which the IOL stability could be compromised
- 7. Patients with preoperative problems such as corneal endothelial disease, abnormal cornea, macular degeneration, retinal degeneration, glaucoma, and chronic drug miosis may not achieve the visual acuity of patients without such problems. The physician must determine the benefits to be derived from lens implantation when such conditions exist.
- 8. A high level of surgical skill is required for intraocular lens implantation. This surgeon should have observed and/or assisted in numerous implantations and successfully completed one or more courses on intraocular lens implantation before attempting to implant intraocular lenses.
- 9. As with any surgical procedure, there is risk involved. Potential complications accompanying cataract or implant surgery may include, but are not limited to the following: corneal endothelial damage, infection (endophthalmitis), retinal detachment, vitritis, cystoid macular edema, corneal edema, pupillary block, cyclitic membrane, iris prolapse, hemorrhage, and persistent glaucoma and secondary surgical intervention. Secondary surgical interventions include, but are not limited to: lens repositioning, lens replacement, vitreous aspiration or iridectomy for pupillary block, wound leak repair, and retinal detachment repair.
- 10. Care should be taken to remove viscoelastic from the eye at the close of surgery.

### PACKAGING/STERILIZATION

The enVista IOL is individually packaged in a pouch and plastic vial that should be opened under sterile conditions. The lens is stored in 0.9% sterile saline solution within the top cavity on the vial. A patient card and self adhesive labels are supplied to provide traceability of the IOL. The enVista IOL is sterilized by gamma-sterilization.

**HOW SUPPLIED**

The lens is supplied sterile in a screw-cap vial (containing a 0.9% saline solution), within a peel pouch. The package is sterilized by gamma irradiation and should be opened only under sterile conditions.

**EXPIRATION DATE**

Sterility is guaranteed unless the pouch is damaged or opened. The expiration date on the lens package is the sterility expiration date. This lens should not be implanted after the indicated sterility expiration date.

**ADVERSE EVENT REPORTING**

Adverse events and/or potentially sight threatening complications that may be regarded as lens related and that were not previously expected in nature, severity or degree of incidence should be reported within five (5) days to Bausch & Lomb Incorporated. This information is being requested from all surgeons in order to document potential long-term effects of intraocular lens implantation.

Physicians are encouraged to report these events in order to aid in identifying emerging or potential problems with intraocular lenses. These problems may be related to a specific lot of lenses or may be indicative of long-term effects associated with these lenses or with IOLs in general. If you wish to report a problem, please call Bausch + Lomb at [name].

**PATIENT REGISTRATION INSTRUCTIONS AND REPORTING REGISTRATION**

Each patient who receives an enVista IOL must be registered with Bausch + Lomb at the time of lens implantation. Registration is accomplished by completing the Implant Registration Card that is enclosed in the lens package and mailing it to Bausch + Lomb. Patient registration is essential and will assist Bausch + Lomb in responding to adverse reaction reports and/or potentially sight-threatening complications. An implant identification card is supplied in the lens package and must be given to the patient.

**RETURNED GOODS POLICY**

All lenses being returned must be accompanied by a returned goods authorization number issued by Bausch + Lomb Customer Service. Call [name] for return authorization and full policy information.

**WARRANTY**

Bausch & Lomb Incorporated warrants that the intraocular lens, when delivered, will conform to all applicable laws and the manufacturer's then current version of the published specifications for such intraocular lens in all material respects and will be free from defects in material and workmanship.

**BAUSCH & LOMB INCORPORATED DISCLAIMS ALL OTHER WARRANTIES, EXPRESS, IMPLIED OR BY OPERATION OF LAW, INCLUDING, BUT NOT LIMITED TO, ANY IMPLIED WARRANTY OF MERCHANTABILITY OR FITNESS FOR A PARTICULAR PURPOSE. BAUSCH + LOMB INCORPORATED SHALL NOT BE LIABLE FOR ANY INCIDENTAL, CONSEQUENTIAL, INDIRECT OR EXEMPLARY DAMAGES OF ANY KIND, DIRECTLY OR INDIRECTLY ARISING FROM THE PURCHASE OR USE OF THIS PRODUCT EVEN IF BAUSCH & LOMB INCORPORATED HAD BEEN ADVISED OF THE POSSIBILITY OF SUCH LOSS, DAMAGE OR EXPENSE.**

**SYMBOLS USED ON LABELING**

Symbol	Description	Symbol	Description
IOL	Intraocular Lens	⌚	Do Not Reuse
PC	Posterior Chamber	📅	Use By (YYYY-MM: year-month)
PCL	Posterior Chamber Lens	𝛾 STERILE	Gamma Sterilized
UV	Ultraviolet	Rx ONLY	Caution: Federal (US) law restricts this device to sale by or on the order of a physician
D	Diopter	⚠	Caution: Consult Instructions for Use
Ø B	Body Diameter (Optic Diameter)	🌡	Storage Temperature Limitation
Ø T	Overall Diameter (Overall Length)	⌚	Do Not Resterilize
SN	Serial Number	MEMBER GREEN DOT	Member Green Dot Scheme

Bausch & Lomb Incorporated, [name] USA

EC REP

Bausch & Lomb Incorporated, [name]

Manufacturing Site:  
Bausch & Lomb Incorporated  
[name]

U.S. Patents: 6281319 and 6635731.

®/TM are trademarks of Bausch & Lomb Incorporated or its affiliates.

© Bausch & Lomb Incorporated.

CE 1275

TEAE	Treatment-Emergent Adverse Event
TE-SAE	Treatment-Emergent Serious Adverse Event
UCDVA	Uncorrected Distance Visual Acuity
UCIVA	Uncorrected Intermediate Visual Acuity
UCNVA	Uncorrected Near Visual Acuity
VA	Visual Acuity
WHO	World Health Organization

2 Introduction

This statistical analysis plan (SAP) has been written in support of protocol number 945 (Version 8.0, 24 April 2023) and finalized before any analyses of the data. The SAP contains detailed information to aid in the performance of the statistical analyses and reporting of the study data for use in the final clinical study report (CSR). This SAP was written with due consideration of the recommendations outlined in the most recent International Conference on Harmonization (ICH) E9 Guideline entitled: Statistical Principles for Clinical Trials, the most recent ICH E3 Guideline entitled: Structure and Content of Clinical Study Reports, and International Organization for Standardization (ISO) 11979-7:2018.

This SAP describes the data that will be analyzed and the subject characteristics, efficacy, and safety assessments that will be evaluated. This SAP provides details of the specific statistical methods that will be used. If additional analyses are required to supplement the planned analyses described in this SAP, they may be completed and will be identified in the CSR.

3 Study Objective and Clinical Parameters

3.1 Study Objective

The objective of this study is to evaluate the safety and effectiveness of the enVista trifocal intraocular lens (IOL) when implanted in the capsular bag.

3.2 Study Endpoints

3.2.1 Primary Safety Endpoints

Primary safety endpoints are:

- The incidence of all serious adverse events (SAEs), including secondary surgical interventions (SSIs) related to the optical properties of the IOL, in first eyes through study exit
- Rate of SSIs due to the optical properties of the IOL for first eyes through study exit
- The incidence of treatment-emergent adverse events (TEAEs) in first eyes compared to International Organization for Standardization (ISO) safety and performance endpoint (SPE) rates as defined in ISO 11979-7:2018 through study exit.

3.2.2 Secondary Safety Endpoints

Secondary Safety Endpoints are:

- The rate of visual disturbances reported as “severe” by subjects as well as the rate of visual disturbances reported as “very” bothersome by subjects using the quality of vision (QoV) questionnaire through Post-Operative Visit 4 (Day 120 to 180 after second eye IOL implantation).
- Mean photopic contrast sensitivity with glare and mesopic contrast sensitivity with and without glare at Post-Operative Visit 4 (Day 120 to 180 after second eye IOL implantation) and Post-Operative Visit 5 (Day 330 to 420 after second eye IOL implantation).

- Incidence of the types of AEs specified in the co-primary endpoints, but for second and “all” eyes
- Incidence of all other types of adverse events in first eyes, second eyes, and “all” eyes

3.2.3 Primary Effectiveness Endpoints

Primary effectiveness endpoints are:

- Photopic monocular best-corrected distance visual acuity (BCDVA; logarithm of the minimum angle of resolution [logMAR]) in first eyes at Post-Operative Visit 4 (Day 120 to 180 after second eye IOL implantation)
- Photopic monocular distance-corrected near visual acuity (DCNVA; logMAR) in first eyes at 40 cm at Post-Operative Visit 4 (Day 120 to 180 after second eye IOL implantation)
- Photopic monocular distance-corrected intermediate visual acuity (DCIVA; logMAR) in first eyes at 66 cm at Post-Operative Visit 4 (Day 120 to 180 after second eye IOL implantation)

3.2.4 Secondary Effectiveness Endpoints

Secondary effectiveness endpoints are:

- Photopic binocular DCNVA (logMAR) at 40 cm at Post-Operative Visit 4 (Day 120 to 180 after second eye IOL implantation)
- Photopic binocular uncorrected near visual acuity (UCNVA; logMAR) at 40 cm at Post-Operative Visit 4 (Day 120 to 180 after second eye IOL implantation)
- Photopic binocular DCIVA (logMAR) at 66 cm at Post-Operative Visit 4 (Day 120 to 180 after second eye IOL implantation)
- Photopic binocular uncorrected intermediate visual acuity (UCIVA; logMAR) at 66 cm at Post-Operative Visit 4 (Day 120 to 180 after second eye IOL implantation)
- Photopic monocular BCDVA (logMAR), DCNVA (logMAR) and DCIVA (logMAR) in first eyes at Post-Operative Visit 5 (Day 330 to 420 after second eye IOL implantation)

3.2.6 Other Safety Assessments

Other safety assessments are:

- Rate of eyes with visual acuity (VA) decreases of 10 letters or more between a visit and a later visit evaluation
- Adverse Events (AEs)
- Intraocular pressure (IOP) by visit
- Slit-lamp exam results by visit
- Dilated fundus exam results by visit
- Posterior capsulotomy assessment results by visit

3.2.7 Other Assessments

Other assessments are:

- Pupil size by visit
- Keratometry by visit
- Manifest refraction by visit
- IOL tilt and decentration by visit
- Chord length at Post-Operative Visit 4 (Day 120 to 180 after second eye IOL implantation) and Post-Operative Visit 5 (Day 330 to 420 after second eye IOL implantation)
- QoV questionnaire at Post-Operative Visit 4 (Day 120 to 180 after second eye IOL implantation)
- Near Activity Visual Questionnaire (NAVQ) at Post-Operative Visit 4 (Day 120 to 180 after second eye IOL implantation) (Use of the exploratory NAVQ subject questionnaire will be discontinued after written FDA acceptance of the protocol)

Version 5 [Version date 23 April 2021], with the exception that subjects who have completed the NAVQ pre-operatively at the time of NAVQ discontinuation also will be asked to complete the NAVQ at Post-Operative Visit 4 [120 days to 180 days after second IOL implantation]]

- Prolonged use of anti-inflammatory medication beyond 6 weeks
- Trial frame astigmatism sub study assessments (photopic monocular BCDVA, DCIVA, and DCNVA) at Post-Operative Visit 6 (Day 2 to 30 post Visit 5)

3.3 Statistical Hypotheses

3.3.1 First Primary Safety Endpoint

There is no statistical hypothesis associated with the proportion of first eyes in the modified safety set with at least one SAE.

3.3.2 Second Primary Safety Endpoint

The second primary safety endpoint is the rate of SSIs due to the optical properties of the lens. The null (H_0) and alternative (H_1) hypotheses are as follows:

$$H_0: \pi_T - \pi_C \geq 0.034$$
$$H_1: \pi_T - \pi_C < 0.034$$

Where:

- π_T = the proportion of the Test (trifocal) group in the first eyes that underwent at least one SSI related to the optical properties of the IOL;
- π_C = the proportion of the Control (monofocal) group in the first eyes that underwent at least one SSI related to the optical properties of the IOL; and
- 0.034 is the non-inferiority margin.

3.3.3 Third Primary Safety Endpoint

The third primary safety endpoint is the incidence of TEAEs in first Test (trifocal) eyes compared to ISO SPE rates as defined in ISO 11979-7:2018. For each ISO 11979-7 SPE grid AE, the null (H_0) and alternative (H_1) hypotheses are as follows:

$$H_0: \pi \leq \pi_0$$
$$H_1: \pi > \pi_0$$

Where:

- π = the proportion of Test (trifocal) eyes with the AE; and
- π_0 = the historical control proportion of eyes with the AE given in the ISO 11979-7 SPE grid.

If none of the null hypotheses are rejected, then it will be concluded that the Test IOL is statistically successful in these outcomes.

3.3.4 Secondary Safety Endpoints

First Secondary Safety Endpoint

There is no hypothesis associated with the incidence of subjects reporting rates of visual disturbances reported as “severe” by subjects, as well as the rates of visual disturbances reported as “very” bothersome by subjects, using the QoV questionnaire measure through Post-Operative Visit 4 (Day 120 to 180 after second eye IOL implantation).

Second Secondary Safety Endpoint

There is no hypothesis associated with mean photopic or mesopic contrast sensitivity at Post-Operative Visit 4 (Day 120 to 180 after second eye IOL implantation) and Post-Operative Visit 5 (Day 330 to 420 after second eye IOL implantation)

Third and Fourth Secondary Safety Endpoints

There are no hypotheses associated with these endpoints.

3.3.5 Primary Effectiveness Endpoints

The statistical success of the trial will depend on the statistical success of all three primary effectiveness endpoints.

First Primary Effectiveness Endpoint

For the first primary effectiveness endpoint, photopic monocular logMAR BCDVA in first eyes at Post-Operative Visit 4 (Day 120 to 180 after second eye IOL implantation), there are three hypotheses to be tested. The Test IOL must be successful in all three hypothesis tests to achieve success in this endpoint.

The first null (H_0) and alternative (H_1) hypotheses are as follows:

$$H_0: \mu_T - \mu_C \geq 0.10$$
$$H_1: \mu_T - \mu_C < 0.10$$

Where:

- μ_T = the mean logMAR BCDVA of the Test (trifocal) group
- μ_C = the mean logMAR BCDVA of the Control (monofocal) group
- 0.10 is the non-inferiority margin

If the null hypothesis is rejected, then it will be concluded that the Test IOL is statistically successful in this evaluation.

The second null (H_0) and alternative (H_1) hypotheses are as follows.

$$H_0: \pi_T \geq 0.925$$

$$H_1: \pi_T < 0.925$$

Where π_T = the proportion of mITT Set Test (trifocal) group eyes with BCDVA 20/40 or better. The ISO standard specifies a nontraditional evaluation of these hypotheses, with failure to reject the null hypothesis indicating success. If the null hypothesis is not rejected, then it will be concluded that the Test IOL is statistically successful in this evaluation.

The third null (H_0) and alternative (H_1) hypotheses are as follows.

$$H_0: \pi_T \geq 0.967$$
$$H_1: \pi_T < 0.967$$

Where π_T = the proportion of Best Case Set Test (trifocal) group eyes with BCDVA 20/40 or better. The ISO standard specifies a nontraditional evaluation of these hypotheses, with failure to reject the null hypothesis indicating success. If the null hypothesis is not rejected, then it will be concluded that the Test IOL is statistically successful in this evaluation.

Second Primary Effectiveness Endpoint

For the second primary effectiveness endpoint, photopic monocular logMAR DCNVA in first eyes at Post-Operative Visit 4 (Day 120 to 180 after second eye IOL implantation), the null (H_0) and alternative (H_1) hypotheses are as follows:

$$H_0: \mu_T = \mu_C$$
$$H_1: \mu_T \neq \mu_C$$

Where:

- μ_T = the mean logMAR DCNVA of the Test (trifocal) group
- μ_C = the mean logMAR DCNVA of the Control (monofocal) group

If the null hypothesis is rejected and the mean for the Test group is less than the mean for the Control group, then it will be concluded that the Test IOL is statistically successful in this outcome.

Third Primary Effectiveness Endpoint

For the third primary effectiveness endpoint, photopic monocular logMAR DCIVA in first eyes at Post-Operative Visit 4 (Day 120 to 180 after second eye IOL implantation), the null (H_0) and alternative (H_1) hypotheses are as follows:

$$H_0: \mu_T = \mu_C$$
$$H_1: \mu_T \neq \mu_C$$

Where:

- μ_T = the mean logMAR DCIVA of the Test (trifocal) group
- μ_C = the mean logMAR DCIVA of the Control (monofocal) group

If the null hypothesis is rejected and the mean for the Test group is less than the mean for the Control group, then it will be concluded that the Test IOL is statistically successful in this outcome.

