### **13.5.3.3 Photopic Monocular DCIVA**

Photopic monocular distance-corrected intermediate visual acuity (DCIVA) at 66 cm in first eyes at Post-Operative Visit 4 will be converted from letters correct to logMAR units using the method described above for BCDVA and summarized using continuous summary statistics in logMAR units by treatment assignment for the mITT Set Phase II and III subjects (combined). The DCIVA data from the Phase I/Pilot subjects will be excluded from hypothesis testing and will be summarized separately from the data of the other subjects.

If there are missing mITT analysis set monocular DCIVA data at Visit 4, then missing data will be imputed using the MCMC multiple imputation method. After imputation of missing data, the statistical hypotheses will be tested using a statistical model with treatment and site as fixed factors by imputation.

An overall p-value resulting from the multiple imputation method will be estimated. The treatment effect (mean Test group IOL VA minus mean Control group IOL VA) in logMAR units will be summarized using continuous summary statistics and a two-sided 95% confidence interval. If the p-value from the multiple imputation analysis is less than or equal to 0.05 and the treatment effect is less than or equal to -0.10 (i.e. the Test lens mean logMAR VA is at least 0.10 less than the mean for the control), then it will be concluded that the Test IOL is statistically and clinically successful (i.e., superior to control) in this outcome.

The previous continuous summary statistics will also be provided for the Per Protocol Set. However, superiority will not be evaluated with the PP Set and statistical success will not depend upon the results of the PP analysis

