6.4 Primary Effectiveness Endpoints

Approximately the first 24 evaluable Test group subjects and 12 evaluable Control group subjects will be excluded from the near and intermediate VA hypothesis tests, leaving an expected evaluable sample size of approximately 276 Test group subjects and 138 Control group subjects to be included in the near and intermediate visual acuity hypothesis tests.

Regarding the non-inferiority test of BCDVA, when the sample sizes in the groups are 300 (Group 1) and 150 (Group 2), a two group 0.050 one-sided t-test will have 99% power to reject the null hypothesis that the Test and Control IOLs are not equivalent (the difference in means, $\mu_T - \mu_S$, is 0.10 or farther from zero in the same direction) in favor of the alternative hypothesis that the means of the two groups are equivalent, assuming that the expected difference in means is 0.00 and the common SD is 0.15.

Regarding the comparisons of BCDVA to the ISO grid, ISO 11979-7 specifies a sample size of approximately 300 completed subjects for this type of investigation.

Regarding the superiority tests of DCNVA at 40 cm and DCIVA and 66 cm, a two-group t-test with a 0.05 two-sided significance level will have 99% power to detect a difference in means of -0.10, assuming that the common SD is 0.15, when the sample sizes in the two groups are 276 and 138 subjects, respectively (a total sample size of 414 subjects).

Regarding the assessment of clinical superiority in DCNVA at 40 cm and DCIVA at 66 cm, the probability that the Test group's mean logMAR VA will be at least 0.10 units less than the Control group's mean logMAR VA will be 89% if the true difference is -0.12 units, 97% if the true difference is -0.13 units, and 99% if the true difference is -0.14 units, assuming that the common standard deviation is 0.15 when the sample sizes in the two groups are 276 and 138 subjects, respectively (a total sample size of 414 subjects).

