6.5 Secondary Effectiveness Endpoints

Secondary effectiveness endpoint hypotheses will be tested hierarchically in the order: DCNVA, UCNVA, DCIVA, and UCIVA. Approximately the first 24 evaluable Test group (Group 1) subjects and 12 evaluable Control group (Group 2) subjects will be excluded from the near and intermediate visual acuity hypothesis tests, leaving an expected evaluable sample size of approximately 276 Test group subjects and 138 Control group subjects to be included in the near and intermediate VA hypothesis tests.

Regarding photopic binocular distance-corrected near visual acuity (DCNVA) at 40 cm at Post-Operative Visit 4 (Day 120 to 180 after second eye IOL implantation), a two-group t-test with a 0.05 two-sided significance level will have 99% power to detect a difference in means of -0.10 logMAR units, assuming that the common SD is 0.200 units, when the sample sizes in the two groups are 276 and 138 subjects, respectively (a total sample size of 414 subjects).

Regarding photopic binocular uncorrected near visual acuity (UCNVA) at 40 cm at Post-Operative Visit 4 (Day 120 to 180 after second eye IOL implantation), a two group t-test with a 0.05 two-sided significance level will have 99% power to detect a difference in means of -

0.10 logMAR units, assuming that the common SD is 0.20 units, when the sample sizes in the two groups are 276 and 138 subjects, respectively (a total sample size of 414 subjects).

Regarding photopic binocular distance-corrected intermediate visual acuity (DCIVA) at 66 cm at Post-Operative Visit 4 (Day 120 to 180 after second eye IOL implantation), a two group t-test with a 0.05 two-sided significance level will have 99% power to detect a difference in means of -0.10 logMAR units, assuming that the common SD is 0.15 units, when the sample sizes in the two groups are 276 and 138 subjects, respectively (a total sample size of 414 subjects).

Regarding photopic binocular uncorrected intermediate visual acuity (UCIVA) at 66 cm at Post-Operative Visit 4 (Day 120 to 180 after second eye IOL implantation), a two group t-test with a 0.05 two-sided significance level will have 99% power to detect a difference in means of -0.10 logMAR units, assuming that the common SD is 0.20 units, when the sample sizes in the two groups are 276 and 138 subjects, respectively (a total sample size of 414 subjects).

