13.3.2 Photopic Monocular DCNVA

Phase I/Pilot subjects will be excluded from the analysis of this endpoint.

Photopic monocular DCNVA (logMAR) at 40 cm in first eyes at Post-Operative Visit 4 (Day 120 to 180 after second eye IOL implantation) will be summarized using continuous summary statistics in logMAR units by treatment assignment for the mITT Set.

If there are missing mITT Set monocular DCNVA data in first eyes at Post-Operative Visit 4 (Day 120 to 180 after second eye IOL implantation), then missing data will be imputed using the MCMC multiple imputation method. A total of 30 imputation datasets will be created. After imputation of missing data, the statistical hypotheses will be tested using an ANCOVA model with treatment and site as fixed factors by imputation.

SAS® code for the MCMC multiple imputation:

```
PROC MI DATA=indata OUT=mcmc NIMPUTE=30 SEED= 1091148178;  
  BY trt;  
  MCMC INITIAL=EM;  
  VAR V3 V4;  
  RUN;
```

where

- trt = treatment
- v3 = actual value at Visit 3A
- v4 = actual value at Post-Operative Visit 4 (Day 120 to 180 after second eye IOL implantation)

An overall p-value resulting from the multiple imputation method will be estimated. The treatment effect (LS mean for Test group IOL VA minus LS mean Control group IOL VA) in logMAR units and a two-sided 95% CI will be provided. If the p-value from the multiple imputation analysis is less than or equal to 0.05 and the treatment effect is less than or equal to -0.10 (i.e., the Test lens mean logMAR VA is at least 0.10 less than the mean for the control), then it will be concluded that the Test IOL is statistically and clinically successful (i.e., superior to the Control IOL) in this outcome.

The previous continuous summary statistics will also be provided for the PP Set. However, superiority will not be evaluated with the PP Set, and statistical success will not depend upon the results of the PP analysis.

As a sensitivity analysis, observed DCNVA (logMAR) at 40 cm in first eyes at Post-Operative Visit 4 (Day 120 to 180 after second eye IOL implantation) will be compared between treatment groups using an ANCOVA model with treatment and site as fixed factors. The treatment effect (LS mean for Test group IOL VA minus LS mean Control group IOL VA) in logMAR units and a two-sided 95% CI will be provided. The analysis will be for the ITT set.

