13.4.4 Photopic Binocular UCIVA

Phase I/Pilot subjects will be excluded from the analysis of this endpoint.

Photopic binocular DCIVA (logMAR) at 66 cm at Post-Operative Visit 4 (Day 120 to 180 after second eye IOL implantation) will be analyzed similarly to the analyses of the second primary effectiveness endpoints described in [Section 13.3.2](#) using a seed of 1303271003 for imputation of missing data.

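### DCNVA and DCIVA each have two success rules, with and without an effect threshold, and the documents do not consistently say which one decides trial success and opens the secondary tests

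*SAP*

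**What the plan says.** **Direction-only rule.** SAP 3.3.5 calls DCNVA and DCIVA statistically successful on this condition: "If the null hypothesis is rejected and the mean for the Test group is less than the mean for the Control group". Protocol 13.2.2 says the same. No effect size is required. The section opens with "The statistical success of the trial will depend on the statistical success of all three primary effectiveness endpoints". SAP 3.3.6 opens the secondary sequence once the lens is statistically successful on all primary endpoints that have success criteria, and SAP 9.4 refers to Section 3.3 for those criteria.

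**Threshold rule.** SAP 13.3.2 (DCNVA) draws its conclusion only if the p-value "is less than or equal to 0.05 and the treatment effect is less than or equal to -0.10". SAP 13.3.3 applies the same method to DCIVA. Protocol 13.5.3.3 sets the same DCIVA condition, in part "0.05 and the treatment effect is less than or equal to -0.10 (i.e. the Test lens mean logMAR VA". Protocol 13.5.3.2 uses -0.20 for DCNVA. A lens that meets both conditions is called statistically and clinically successful, and SAP 13.3.2 and Protocol 13.5.3.2–13.5.3.3 gloss that as superior to control. The synopsis repeats the two thresholds without the gloss.

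**Where the trial-success sentence sits.** In SAP 3.3.5 and Protocol 13.2.2 it stands over the direction-only rule. In the synopsis it opens the primary effectiveness analyses, where the threshold rule is the only DCNVA/DCIVA criterion. Protocol 13.6.3 refers to Section 13.1 for success criteria, but 13.1 only lists endpoints.

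**The concern.** A decision rule for a co-primary endpoint should give one answer for any result. Here a significant DCIVA gain below 0.10 is a statistical success under one section, yet it does not meet the condition that another section sets for concluding superiority. The synopsis sample-size text gives superiority in DCNVA and DCIVA as the primary objective. If the direction-only rule governs, the clinical threshold changes nothing about trial success or the secondary gate. If the threshold rule governs, SAP 3.3.5, SAP 9.4 and Protocol 13.2.2 state the wrong criterion.

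The problem is separate from the disagreement over the DCNVA threshold, because it also affects DCIVA, where both documents use -0.10. The table of changes in SAP Section 16 has three entries, all on safety analysis populations, and does not address it.

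**Working it through.** Gains are Control minus Test in logMAR, so a gain of 0.10 is a treatment effect of -0.10.

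**Inputs (SAP 6.4).** The power statement is "a two-group t-test with a 0.05 two-sided significance level will have 99% power to detect a difference in means of -0.10". Its other inputs are an SD of 0.15 and evaluable groups of 276 (Test) and 138 (Control). The same section gives probabilities of 89%, 97% and 99% of observing a gain of at least 0.10 when the true differences are -0.12, -0.13 and -0.14.

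**Standard error.** SE = 0.15 × √(1/276 + 1/138) = 0.01564.

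**The plan's own figures.**
- Two-sided t-test power at a true 0.10: above 99.9% (0.999995), consistent with the stated 99%.
- P(observed gain ≥ 0.10) = Φ((true gain − 0.10)/SE): 90.0%, 97.2% and 99.5% at 0.12, 0.13 and 0.14, against the stated 89%, 97% and 99%.

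**Smallest significant gain.** t(0.975; 412 df) × SE = 0.0307. An observed gain of 0.030 gives p = 0.056, and 0.031 gives p = 0.048. The rules therefore disagree for observed DCIVA gains from about 0.031 up to, but not including, 0.10. A gain of exactly 0.10 meets both.

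**Chance of success by true gain.** Direction-only: Φ((true gain − 0.0307)/SE). Threshold: Φ((true gain − 0.10)/SE). The probability that the rules diverge is the difference.

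| True DCIVA gain | Direction-only | With 0.10 threshold | Rules diverge |
|---|---|---|---|
| 0.07 (assumed) | 99.4% | 2.8% | 96.6% |
| 0.10 (SAP 6.4, power) | >99.9% | 50.0% | 50.0% |
| 0.12 (SAP 6.4) | >99.9% | 90.0% | 10.0% |
| 0.13 (SAP 6.4) | >99.9% | 97.2% | 2.8% |
| 0.14 (SAP 6.4) | >99.9% | 99.5% | 0.5% |

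**Sensitivity to the SD.** The lower end of the band is 0.020 at SD 0.10, 0.041 at SD 0.20 and 0.051 at SD 0.25.

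**DCNVA.** At SD 0.15 the band runs from about 0.031 to just below 0.10 under the SAP threshold, or just below 0.20 under the Protocol threshold.

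**Secondary power.** For the endpoints with SD 0.20, SAP 6.5 states "99% power to detect a difference in means of - 0.10 logMAR units, assuming that the common SD is 0.20 units". SE = 0.20 × √(1/276 + 1/138) = 0.02085, and the t-test power at 0.10 is 99.8%. The stated figure is correct for that test.

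**The case against.** The strongest reply is that the SAP does give an answer. Trial success depends on statistical success, SAP 3.3.5 defines that by direction and significance, and SAP 9.4 refers to Section 3.3 for the criteria. The labels also differ: one rule yields statistical success, the other statistical and clinical success. The sample-size text likewise treats the test of difference and the assessment of clinical superiority separately. On this reading there are two tiers and no contradiction.

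Much of that stands. A reader might infer that the SAP is silent on which rule governs, or that a DCIVA gain in the band both wins and loses the trial. The documents do not support either inference: the SAP read literally points to the direction-only rule, and nowhere is it said that the trial fails if the threshold is missed.

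The reply does not clear up the rest. The body sections attach superiority to the combined rule, and superiority is the primary objective. The synopsis puts the trial-success sentence over the threshold rule alone. The cross-reference in Protocol 13.6.3 leads to a section without criteria. If two tiers are intended, no text says what the clinical tier decides.

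A reader might also extend the conflict to the secondary endpoints, because SAP 13.4.4 says its endpoint "will be analyzed similarly to the analyses of the second primary effectiveness endpoints described in" Section 13.3.2 (13.4.2 does likewise), and conclude that the 99% power for UCNVA and UCIVA should be 50%. That does not hold. SAP 3.3.6 states their success rule without a threshold, and the reference back to 13.3.2 is followed by an imputation seed, so it most naturally imports the model and the imputation.

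**Conclusion.** The point holds as an unresolved decision rule on two of the three co-primary effectiveness endpoints. The SAP's literal reading leaves the clinical threshold without consequence for trial success or the secondary gate. The synopsis ties trial success to the threshold rule, and the Protocol's multiplicity section does not settle the matter.

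The practical size depends on the true effect. If DCIVA performs as in the plan's scenarios of -0.12 to -0.14, the rules give the same answer in about 90% to 99.5% of trials. If the true effect were about -0.07, an assumed value that the documents do not give, they would give different answers about 97% of the time. These figures assume SD 0.15, 276 and 138 evaluable subjects and a simple two-group comparison without the site term or imputation.

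**What to change.** Before treatment unmasking, state one decision rule for each of DCNVA and DCIVA, and use it in SAP 3.3.5, 9.4 and 13.3.2–13.3.3, in Protocol 13.2.2, 13.5.3 and 13.6.3, and in the synopsis. Say explicitly that this rule decides trial success and opens the secondary sequence.

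- **Consistent choice:** significance plus the effect threshold, because superiority is the stated objective and is defined by that combination.
- **Alternative:** if the threshold is meant only as a separate clinical tier, say so, and remove the gloss that equates meeting it with superiority.

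Reconcile the DCNVA threshold (-0.20 or -0.10) at the same time, since the rule cannot be applied without a single value. In Protocol 13.6.3, point to the section that holds the criteria.

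For UCNVA and UCIVA, state that SAP 13.4.2 and 13.4.4 take only the model and imputation from 13.3.2. Also correct the body text of those two sections, which names the distance-corrected variables under uncorrected headings. The 99% power in SAP 6.5 needs no change.

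The cost is wording in both documents. The consistent choice makes the stated route to success stricter; the alternative gives up calling the threshold result superiority. A choice made after unmasking would be post hoc.
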